### 5.2 Secondary Efficacy

The following secondary efficacy endpoints will be analyzed for all randomized patients (i.e., ITT population). Interpretations of significance levels (i.e. P-values) will be done with caution since there is no formal control of type I error for multiple comparisons on the secondary efficacy endpoints.

#### 5.2.1 Mean Maximum Radiation Dermatitis Grade of RTA 408 Lotion Compared to Administration of Vehicle

The first secondary efficacy endpoint is the mean maximum dermatitis grade. A maximum CTCAE grade per patient evaluated at weekly visits during the study will be identified.

Descriptive statistics will be summarized for the maximum dermatitis grade overall and by each of the subgroups of interest, breaking down by the 3 treatment groups.

An analysis of Covariance (ANCOVA) model will be conducted to compare the mean maximum dermatitis grade among the RTA408 0.5%, RTA408 3% and vehicle groups, adjusted for site, smoking status, breast cancer treatment prior to radiation therapy and total duration (in weeks) of study drug use. Pairwise RTA 408 lotion group comparisons with vehicle group will be estimated using the difference in adjusted means (and 95% confidence intervals, CI) from the ANCOVA model.

### **5.2.2 Proportion Patients with Post-baseline Maximum Dermatitis Grade <2 Using the CTCAE Criteria**

Descriptive statistics (frequencies and percentages) by treatment groups will be provided overall and stratified by smoking status and breast cancer treatment prior to radiation therapy, respectively. In addition, logistic regression analysis will be performed to assess the dermatitis scores over time for the proportion of patients with success, where success is defined as CTCAE dermatitis score <2. The logistic regression model will include covariates for site, smoking status (smoker or ex-smoker vs non-smoker) and breast volume with fixed effects for treatment group, visit, and the interaction between treatment group and visit. To visualize the grade patterns in RTA408 groups and the vehicle group, a bar chart will be plotted for the proportions of CTCAE dermatitis scores by treatment groups and study visit.

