6.2. Secondary Study Objectives

The secondary objectives of this study are the following:

1. To determine the mean maximum radiation dermatitis grade measured with CTCAE of RTA 408 Lotion (0.5% and 3%) compared to administration of vehicle
2. To determine the proportion of patients with treatment success, defined as post-baseline maximum dermatitis grade < 2 using the CTCAE criteria following administration of RTA 408 Lotion compared to administration of vehicle
3. To determine the mean duration of grade ≥ 2 radiation dermatitis using the CTCAE criteria following administration of RTA 408 Lotion compared to administration of vehicle
4. To determine the extent of systemic exposure to RTA 408 following administration of RTA 408 Lotion following radiation therapy
5. To evaluate patient-reported outcomes (Skindex-16)

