8.4.2. Patient Study Termination Criteria

Termination refers to a patient stopping study drug and all study assessments and visits. Reasons for patient study termination include the following:

- Failure to return for follow-up
- Death
- Withdrawal of consent
- Investigator decision

Patients who terminate the study for any reason may not re-initiate study drug at any time.

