##### **3.2.1 Intent-to-treat Population (ITT)**

The intent-to-treat (ITT) population includes all randomized patients whether or not they received study drug. Patients will be summarized according to the treatment to which they were randomized.

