### **3.6 Missing Data**

Missing data will not be imputed for safety endpoints. Missing efficacy endpoints will be imputed using the worst-observation reported for each patient. Sensitivity analyses for efficacy endpoints will be performed with no imputation for missing data. Additional sensitivity analyses may be considered as needed.

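### Filling gaps with a patient's own worst grade cannot change her maximum, so a patient who leaves early with only grades 0 or 1 is counted as a treatment success

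*SAP*

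**What the plan says.** Protocol 6.2 makes treatment success a secondary objective, "defined as post-baseline maximum dermatitis grade < 2 using the CTCAE criteria". SAP 5.2.2 carries this as "Proportion Patients with Post-baseline Maximum Dermatitis Grade <2 Using the CTCAE Criteria" and plans two things: frequencies and percentages by arm, and a logistic regression with visit and treatment-by-visit terms in which "success is defined as CTCAE dermatitis score <2". SAP 5.2.1 takes each patient's maximum grade over the weekly visits and compares arm means by ANCOVA.

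On the population, SAP 5.2 states: "The following secondary efficacy endpoints will be analyzed for all randomized patients". SAP 3.2.1 adds: "The intent-to-treat (ITT) population includes all randomized patients whether or not they received study drug".

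On missing data, SAP 3.6 states: "Missing efficacy endpoints will be imputed using the worst-observation reported for each patient". It then adds: "Sensitivity analyses for efficacy endpoints will be performed with no imputation for missing data". Further sensitivity analyses are left open and unspecified.

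On leaving the study, Protocol 8.4.2 states: "Termination refers to a patient stopping study drug and all study assessments and visits". Neither document sets a minimum period of observation for success, requires a grade at or after the end of radiation, or says how an early leaver is classified.

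**The concern.** A per-patient maximum can only rise as more visits are observed, so a patient followed for less time has less chance of recording grade 2. A missing-data rule for such an endpoint has to say something about the unseen visits. The rule in SAP 3.6 looks conservative because it uses the worst value, but for a maximum it does nothing: the patient's later grades are taken to be no worse than those already seen.

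At stake are the headline success percentages and the mean maximum grade. An arm that loses more patients early gains on both, whatever the reason for leaving. The planned sensitivity analysis cannot reveal this, because it returns the same per-patient value.

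**Working it through.** **Inputs.** From the documents: 177 patients in three equal arms (177 / 3 = 59; Protocol 7.2), success as maximum grade below 2, own-worst fill, and no imputation as the sensitivity analysis. The documents as supplied give no expected success rate, dropout rate or weekly grade distribution, so there is no planned figure to reproduce. The sizes below rest on assumed ranges.

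**Step 1: the fill does nothing to a maximum.** Let M be the maximum of a patient's observed grades. The filled series is the observed grades plus copies of M, and its maximum is M. Without imputation the observed maximum is also M. Enumerating grade sequences (grades 0 to 3) gave 0 changes in 5,460 dropout patterns and 0 in 3,124 patterns with intermittent gaps.

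**Step 2: how early a patient can leave and still be a success.** Grades are taken before that day's irradiation (Protocol Table 3, footnote r). Assuming five fractions a week, a patient graded at Visit 5 (radiation week 3) has had 10 fractions.
- 1.8 Gy schedule: 18 Gy of a planned 55 to 66.4 Gy including boost, or 27% to 33%.
- 2 Gy schedule: 20 Gy of 56 to 66 Gy, or 30% to 36%.

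If she then terminates at grade 1 with no later grade, she is a success. At the extreme, SAP 3.7.2 sets baseline before the first dose, so the Visit 3 grade is post-baseline although it precedes any radiation. A patient with only that grade, at 0, is also a success.

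**Step 3: effect on one arm.** Let p be the true success rate (taken as the same in leavers and stayers), d the share leaving early, and q the share of leavers whose recorded grades are all below 2. The credited rate is d·q + (1 − d)·p, so the excess over p is d·(q − p). With q = 1:

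| Early loss d (of 59) | p = 0.20 | p = 0.40 | p = 0.60 |
|---|---|---|---|
| 5% (about 3) | 0.240 (+4.0 points) | 0.430 (+3.0) | 0.620 (+2.0) |
| 10% (about 6) | 0.280 (+8.0) | 0.460 (+6.0) | 0.640 (+4.0) |
| 20% (about 12) | 0.360 (+16.0) | 0.520 (+12.0) | 0.680 (+8.0) |

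**Step 4: unequal loss, no drug effect.** The false difference is (d1 − d2)·(q − p). For 15% against 5% with q = 1:
- p = 0.20: 0.32 − 0.24 = 8 points
- p = 0.40: 0.49 − 0.43 = 6 points
- p = 0.60: 0.66 − 0.62 = 4 points

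If only 80% of leavers are credited (q = 0.8), the range is 0.10 × (0.8 − 0.6) = 2 points to 0.10 × (0.8 − 0.2) = 6 points.

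**Step 5: equal loss, real drug effect.** With q = 1 in both arms, a true difference is multiplied by (1 − d). For 0.30 against 0.50 at d = 10%, the credited rates are 0.37 and 0.55, a difference of 0.18. For an unadjusted two-proportion comparison at 59 per arm, power would fall from 0.60 to 0.50. The SAP plans no such test, so this only conveys scale.

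**Step 6: the opposite rule.** If all these leavers are counted as non-successes, the rate is (1 − d)·p. With 15% against 5% loss and no drug effect, the false difference is −0.10·p, which is 2 to 6 points against the arm with more loss for p from 0.20 to 0.60.

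**The case against.** Several provisions limit the number of patients affected.
- Those who stop only the drug should keep attending visits where possible (Protocol 8.4.1). An adverse event is listed there as a reason for stopping drug, not in 8.4.2 as a reason for leaving the study.
- Poor compliance does not remove a patient from the study (Protocol 9.3).
- The follow-up procedures, which include a dermatitis grade, are also due at early termination (Table 3, footnote h).
- An unscheduled grade can stand in for a missed one (SAP 3.7.3).

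All of this stands and reduces the problem. None of it can record a grade 2 that develops after the last contact.

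A reader might infer that every planned analysis of success is blind to early loss. That goes too far. The logistic model in SAP 5.2.2 is by visit: under the main fill, a grade-1 leaver's later visits all enter as below 2, but without imputation those visits drop out, so the two runs differ. The invariance holds for the per-patient maximum only.

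A reader might also infer that later weeks are treated as free of dermatitis, or that patients are known to leave before the usual peak. The fill assigns the worst grade seen, not grade 0, and neither document says when dermatitis peaks. Nor do the documents show which arm would lose more patients, so no bias towards active lotion can be claimed.

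The ANCOVA in SAP 5.2.1 adjusts for weeks of study drug use, which is related to early leaving. How much this offsets the effect on the mean maximum is not known, so no size is claimed for that endpoint.

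Finally, these are secondary endpoints without type I error control, and SAP 5.2 already urges caution with their p-values.

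**Conclusion.** The point holds for the descriptive per-patient proportion in SAP 5.2.2 and for the mean maximum grade in SAP 5.2.1. For both, the SAP 3.6 rule has no effect and its specified sensitivity analysis gives the same per-patient value. This assumes that, without imputation, the observed maximum is used, as SAP 5.2.1 and the all-available-data rule in SAP 3.1 indicate.

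It applies to patients who leave before the end-of-radiation and early post-radiation assessments with all recorded grades 0 or 1. A leaver already at grade 2 or above is correctly a non-success. A patient with no post-baseline grade has no worst value to use, and SAP 3.7.2 bars filling from baseline, so her status is undefined rather than a success.

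For the success proportion, 15% against 5% early loss gives a false difference of about 4 to 8 points favouring the arm with more loss, for assumed true success of 60% down to 20%, with all leavers credited and leavers otherwise like stayers. Equal loss d shrinks a true difference by the factor (1 − d). If few patients terminate early, the effect is small. The change is worth making before database lock because it uses only data already being collected.

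**What to change.** In SAP 3.6, 5.2.1 and 5.2.2, for the per-patient maximum endpoints only:

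1. Apply the unscheduled-visit substitution of SAP 3.7.3 first.
2. Replace the own-worst fill with multiple imputation of the missing scheduled grades, using arm, visit, observed grades and the two stratification factors. Derive each patient's maximum and success status from the completed series. This also gives a defined status to patients with no post-baseline grade.
3. Add a bounding analysis of success that counts as non-successes the patients with observed maximum below 2 and no grade at or after the end of radiation (Visit 9 or a later scheduled assessment). Judge this by date, because the early-termination assessment shares a schedule column with the follow-up visit.
4. Report the number of such patients by arm.

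The bounding analysis should not become the main rule. It lowers success rates and, as step 6 shows, biases against the arm with more loss, so it should be read beside the imputed result. Accepting any grade at or after Visit 9 avoids failing a patient for one missed visit. The cost is SAP wording and modest extra programming, with no new data collection.

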#### 1.1.2 Secondary Objective

The secondary objectives of this study are the following:

- To determine the mean maximum radiation dermatitis grade measured with CTCAE of RTA 408 Lotion (0.5% and 3%) on weekly visits compared to administration of vehicle
- To determine the proportion of patients with treatment success, defined as post-baseline maximum dermatitis grade  $< 2$  using the CTCAE criteria following administration of RTA 408 Lotion compared to administration of vehicle
- To determine the mean duration of grade  $\geq 2$  radiation dermatitis using the CTCAE criteria following administration of RTA 408 Lotion compared to administration of vehicle
- To determine the extent of systemic exposure to RTA 408 following administration of RTA 408 Lotion following radiation therapy

- To evaluate patient-reported outcomes (Skindex-16)

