### 2.2 Endpoint Measures

#### 2.2.1 Efficacy Endpoints

The primary efficacy endpoint is dermatitis grade (CTCAE v4.03).

The secondary efficacy endpoints are mean maximal dermatitis grade, proportion of patients with maximal dermatitis grade < 2, duration of CTCAE grade  $\geq 2$ , proportion of patients who develop moderate erythema, the proportion of patients who develop dry desquamation and the proportion of patients who develop moist desquamation.

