### **5.2.3 Mean Duration of Grade $\geq 2$ Radiation Dermatitis Using the CTCAE Criteria**

The total duration is defined as the spanning from first onset date with CTCAE grade  $\geq 2$  to last resolved date (i.e., next dermatitis assessment date after the last grade  $\geq 2$ ). Descriptive statistics by treatment groups will be summarized for the total duration, overall and by subgroups of interest for the subset of patients with at least one CTCAE grade  $\geq 2$ . In addition to the descriptive analyses, the mean duration across 3 treatment groups will be compared using an ANCOVA model in a similar manner to the analysis in Session 5.2.1.

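### SAP 5.2.2 gives per-patient treatment success (post-baseline maximum grade <2) only frequencies and percentages; its sole model estimates visit-level success, a different quantity

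*SAP*

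**What the plan says.** Protocol 6.2 sets the objective: "To determine the proportion of patients with treatment success, defined as post-baseline maximum dermatitis grade < 2 using the CTCAE criteria". SAP 1.1.2 repeats it, and SAP 2.2.1 lists the endpoint as the "proportion of patients with maximal dermatitis grade < 2". Each patient therefore contributes one yes/no.

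SAP 5.2.2 carries the same endpoint in its heading. It first provides frequencies and percentages by arm, overall and by each stratification factor. It then adds one model: "logistic regression analysis will be performed to assess the dermatitis scores over time for the proportion of patients with success". For this model the outcome is set on the single score, without reference to the maximum: "where success is defined as CTCAE dermatitis score <2". The model has "covariates for site, smoking status (smoker or ex-smoker vs non-smoker) and breast volume with fixed effects for treatment group, visit", plus the treatment-by-visit interaction. It states no contrast and no within-patient correlation, whereas SAP 5.1 names a subject random effect.

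Four neighbouring provisions matter:

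- SAP 5.2.1 analyses each patient's maximum grade as a mean, adjusting for surgery type among other factors: "Pairwise RTA 408 lotion group comparisons with vehicle group will be estimated using the difference in adjusted means", with 95% CIs.
- SAP 5.2.3 analyses how long grade ≥2 lasts: "The total duration is defined as the spanning from first onset date" of grade ≥2 to the last resolution.
- SAP 5.2.4 sends three further endpoints (patients developing moderate erythema, dry desquamation or moist desquamation) to an analysis like that of 5.2.2.
- Protocol Table 3 (footnote m) and Protocol 9.8.20 schedule breast volume only after breast-conserving surgery. SAP 5.2 says the secondary endpoints are analysed in all randomised patients.

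**The concern.** A patient's maximum grade does not vary by visit, so visit and treatment-by-visit terms have no meaning for it. Followed as written, the model estimates the probability of being below grade 2 at a given visit. Any p-value or confidence interval reported under treatment success would then belong to something else. It could favour an arm that shortens episodes without preventing any, and it could miss a real difference in the proportion of patients who never reach grade 2. The three endpoints in SAP 5.2.4 are also worded per patient, so they too lack a stated per-patient comparison.

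The covariates raise a second question. Mastectomy patients are eligible and form a randomisation stratum, but the model uses a measurement that is not scheduled for them and leaves out the stratum itself.

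**Working it through.** The public copy gives no expected rate for this endpoint, so there is no plan figure to reproduce. The documents supply 59 patients per arm (Protocol 7.2). Every event rate, episode length and mastectomy share below is an assumption.

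**1. The two quantities differ.** Suppose half the patients in each arm ever reach grade ≥2, with eight assessments. Per-patient success is 0.50 in both arms.

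- Episodes lasting one visit: mean visit-level success = 1 − 0.5 × 1/8 = 0.94.
- Episodes lasting four visits: 1 − 0.5 × 4/8 = 0.75.

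Conversely, fix the visit-level rates of grade ≥2 at 1, 3, 8, 18, 32, 45, 30 and 5%. Mean visit-level success is then 0.82 regardless of correlation, but per-patient success runs from 0.18 to 0.52 as the latent within-patient correlation goes from 0 to 0.9. Neither quantity determines the other.

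**2. Equal per-patient success, shorter episodes on active.** Simulation inputs:

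- 59 vs 59, two-sided 5%.
- Assessments at Visits 6–9, 11 and 12.
- Onset of grade ≥2 uniform over Visits 6–9.
- Episodes of 2–4 visits on vehicle; one visit shorter in a stated share of active patients.
- Incidence of grade ≥2 of 50, 65 or 80%, the same in both arms.

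The visit-averaged contrast is the mean over visits of the log-odds difference from the saturated treatment-by-visit model (0.5 added per cell, no covariates), with patient-clustered SEs. The per-patient comparator is a pooled, unadjusted two-proportion test. Ranges run over the three incidences.

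| Active patients with shorter episodes | Visit-averaged rejects | Last-RT-day contrast rejects | Per-patient test rejects |
|---|---|---|---|
| 25% | about 7–12% | about 6–8% | about 5% |
| 50% | about 14–33% | about 10–20% | about 5% |
| 100% | about 50–90% | about 29–60% | about 5% |

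With no shortening, all three reject in about 5%. Adding two earlier visits without grade ≥2 events leaves the table almost unchanged.

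**3. Reverse case: equal episode lengths, per-patient success differs.**

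| Success, vehicle vs active | Per-patient power | Visit-averaged power | Last-RT-day power |
|---|---|---|---|
| 35 vs 50% | about 38% | about 31% | about 23% |
| 35 vs 60% | about 79% | about 69% | about 55% |
| 20 vs 40% | about 67% | about 55% | about 38% |

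**4. Breast volume.** The missing-data rule in SAP 3.6 covers efficacy endpoints, not covariates. The effect therefore depends on coding.

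- Entered as a number with complete-case fitting, all mastectomy patients drop out. At an assumed share of 10–40%, that is 177 × 0.10 = 18 to 177 × 0.40 = 71 patients. The treatment SE grows by 1/√(1 − share): 1/√0.9 = 1.05 to 1/√0.6 = 1.29.
- Coded so that they stay in but have no level of their own, the surgery stratum is unadjusted.
- Coded as volume classes plus a separate mastectomy level, neither problem arises.

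**The case against.** The model is introduced as an addition, after percentages that already show the defined endpoint by arm. SAP 5.2.1 already compares per-patient maximum grade with confidence intervals, and SAP 5.2 promises caution with secondary p-values. All of this stands and limits the consequence. It does not supply a comparison of the proportion below grade 2: a difference in mean maximum grade is not a difference in that proportion.

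The SAP names no contrast, so visit averaging is a choice made for this check. That is fair; the last-RT-day column shows the same direction with smaller effects. A reader might also take the rejections in step 2 as false positives. They are not: the simulated shortening is real. The error would lie in reporting it as treatment success.

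A reader might further infer that the plan excludes mastectomy patients from this analysis. The documents do not say so. SAP 3.4 gives volume classes split at 1200 cc for breast-conservation patients, but as a subset definition; SAP 5.2.2 neither adopts them as the model coding nor says how mastectomy patients are coded. The conflict with the all-randomised statement is conditional on an unstated choice.

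**Conclusion.** The point holds and should be fixed. The mismatch between endpoint and model follows from the text alone. Its size rests on the assumed incidences, episode lengths and contrast, so the simulated figures are illustrations and not predictions for this trial. The covariate problem is an ambiguity with one bad branch, and the size of that branch rests on an assumed mastectomy share.

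Two broader conclusions are not supported. It would be wrong to say the SAP makes no per-patient comparison of dermatitis severity, since SAP 5.2.1 makes one on the mean. It would also be wrong to carry the point to the primary result: this endpoint is secondary, without formal type I error control, and the primary analysis does not use it.

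**What to change.** - **SAP 5.2.2, main analysis:** make it a logistic regression on one record per patient (post-baseline maximum grade <2, yes/no) with treatment, smoking status and prior surgery. Report each RTA 408 versus vehicle comparison with its 95% CI.
- **Site:** leave it out of this binary model. Up to 35 centres (Protocol synopsis) for about 177 patients is 177/35, or about five per site. If site is kept, pool small sites or use a random site effect.
- **Breast volume:** use it only within the breast-conservation subset.
- **Visit-level model:** keep it as supportive, with a patient random effect or GEE and one named contrast, for example the last day of RT or a stated visit average.
- **SAP 5.2.4:** state that the three endpoints use the same per-patient analysis.

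The cost is SAP wording and a simpler program, with no new data. The downside is that a yes/no outcome discards duration information, which SAP 5.2.3 keeps.

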7.2. Number of Patients

Approximately 177 patients (59 per treatment group) are to be enrolled in this study.

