^r Radiation dermatitis assessments must be performed PRIOR to initiation of that day's radiation treatment, and only by a trained evaluator. If radiation treatment is delayed or extended, dermatitis assessments should be performed weekly until the end of radiation treatment.

^s The Skindex-16 must be completed prior to initiation of that day's radiation treatment.

^t Screening lab assessments (described in Section 9.8 for [chemistry](#), [hematology](#), [urinalysis](#), and [serum pregnancy tests](#)) should be drawn ≤ 14 days prior to randomization in order to have current values for inclusion/exclusion assessment.

^u A single PK collection will be obtained on Visit 3, Visit 6, Visit 9, Visit 11 and Visit 12. If patients are to receive a morning radiation treatment on any of these visits, the PK sample should be drawn after RTA 408 Lotion or Vehicle Lotion application, which occurs after the completion of radiation treatment. If patients are to receive an afternoon radiation treatment on any of these visits, the PK sample should be drawn after the radiation treatment.

^v Optional photographs may be collected at Sponsor-qualified sites. On Day 1 of radiation treatment and the last day of radiation treatment, photographs must be collected prior to radiation treatment.

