### 5.1 Primary Efficacy

The primary efficacy outcome of this study is the radiation dermatitis grade measured with Common Terminology Criteria for Adverse Events (CTCAE, Version 4.03) following 3D conformal radiation therapy to the breast and concomitant administration of RTA 408 Lotion (0.5% and 3%) compared to administration of vehicle. Radiation dermatitis scoring is assessed by a local, trained physician, nurse or appropriately trained site staff member based on CTCAE v4.03 on a scale of 0 to 5 (National Cancer Institute, 2010). Following randomization, patients will be evaluated in person at weekly visits during the administration of the study treatment up to a maximum of 13 weeks.

Longitudinal mixed-models will be used to analyze the dermatitis scores over time, incorporating the repeated measures design of the study. Treatment group and week of visit will constitute the main fixed effects of the model; study subject will represent the random effect; site, smoking status, and breast cancer treatment will be evaluated for inclusion in the model as covariates. The distribution of residuals will be examined using a Shapiro-Wilks test. Interactions of time and treatment effect will also be examined in the mixed-model.

A sensitivity analysis will be performed using the same model, except cumulative radiation (expressed as a categorical variable in 2.5 Gy increments from 0 to 70 Gy) will be used as a fixed effect instead of visit week. Only those CTCAE grades collected from baseline to the last day of radiation treatment for each patient will be considered for this sensitivity analysis.

The mean CTCAE dermatitis scores will also be plotted in a scatter plot by cumulative radiation exposure overall and by patient subsets of interest.

RTA 408 treatment arms will be compared with vehicle utilizing a hierarchical testing strategy described in Section 3.6.

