### **5.2.4 Dermatitis Assessment**

Proportion of patients who develop moderate erythema, the proportion of patients who develop dry desquamation and the proportion of patients who develop moist desquamation (according to eCRF) will be analyzed in a similar manner to the analysis in Session 5.2.2.

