- a The Screening Period (Visit 1) may last up to 45 days prior to Randomization (up to 52 days prior to Day 1 of RT).
- b Visit 2 (7 days prior to radiation treatment) is the day of randomization and application of the first dose, and must occur at least 5 and no more than 9 days prior to the first day of radiation treatment. If the start of radiation treatment is delayed, patients should continue administering study drug twice daily until the first dose of radiation up to a maximum of 14 days. If the time from randomization to first dose of radiation exceeds 14 days, the medical monitor should be contacted to decide on an appropriate action. Patients may be randomized after meeting the inclusion / exclusion criteria and before study drug lotion is first administered as long as patients apply study drug lotion for at least 5 days prior to the first day of radiation treatment. Patients with either morning or afternoon randomizations may apply lotion in the clinic and again before bedtime for two doses on that day.
- c Visit 3 should occur on the day of the first radiation treatment. If radiation treatment is in the morning, the radiation treatment will be the third to last procedure (radiation treatment > study drug application > PK). If radiation treatment is in the afternoon, radiation treatment will be the second to last procedure, and the last procedure will be PK, as study drug will have been applied at least 4 hours prior to radiation treatment.
- d Study visits during radiation treatment therapy must occur weekly beginning with Day 1 of radiation treatment.
- e At the end of radiation treatment, patients must complete Visit 9 assessments. Visit 9 must be the last day of the 10 – 16 Gy boost. Visit 8 is needed for patients who require radiation therapy for 6 weeks. If radiation therapy is extended longer than 6 weeks, then assessments at Visit 8 should be repeated weekly until the end of radiation visit (Visit 9). A weekly study visit should not be performed if the visit falls 1 or 2 days prior to the last day of radiation (Visit 9), or 1-2 days after the last day of radiation.
- f Visit 10 should occur approximately 1 week (7 calendar days) after the completion of radiation therapy (Visit 9).
- g Visit 11 should occur approximately 1 week (7 calendar days) after Visit 10 (*i.e.*, 2 weeks after the completion of radiation therapy).

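### SAP 5.2.2's by-visit logistic model has no within-patient term, so a visit-averaged treatment effect gets standard errors that are too small, and including pre-radiation Visit 3 can leave it with no finite estimate

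*SAP*

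**What the plan says.** SAP 5.2.2 covers the treatment-success endpoint. Besides frequencies and percentages, it states that "logistic regression analysis will be performed to assess the dermatitis scores over time for the proportion of patients with success". Each record is classed by its own grade, "where success is defined as CTCAE dermatitis score <2". Covariates are site, smoking status and breast volume, "with fixed effects for treatment group, visit, and the interaction between treatment group and visit". With visit in the model, each patient supplies several records. No patient effect, working correlation or robust variance is named, and neither the visits that enter nor the treatment contrast is stated.

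SAP 5.1, for the primary endpoint, does name one: "study subject will represent the random effect". The protocol gives a model only for the primary endpoint, so it does not fill the gap.

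On timing, SAP Appendix 1 says "Visit 3 should occur on the day of the first radiation treatment", and this is the first scheduled dermatitis assessment. Protocol Table 3, footnote r, adds "Radiation dermatitis assessments must be performed PRIOR to initiation of that" day's radiation. SAP 3.7.2 puts baseline before the first lotion dose, about a week earlier, which makes Visit 3 post-baseline. The sensitivity analysis in SAP 5.1 uses grades from baseline onward, which suggests that Visit 3 may serve as the dermatitis baseline. The SAP does not settle this.

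SAP 5.2.4 says that erythema, dry desquamation and moist desquamation "will be analyzed in a similar manner to the analysis in Session 5.2.2".

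**The concern.** Grades from one patient at successive weekly visits are correlated. An ordinary logistic fit counts them as independent information, so a treatment effect pooled over visits looks more precise than it is.

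A second problem comes from the treatment-by-visit interaction. It gives each arm its own parameter at each visit. If no patient is at grade ≥2 at a visit, those parameters have no finite maximum-likelihood estimate.

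At stake are the nominal p-values and confidence intervals for treatment success, a protocol-listed secondary objective for which this is the only inferential analysis given. The endpoints of SAP 5.2.4 are affected too if they are modelled by visit.

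**Working it through.** **Inputs from the documents.** Protocol 7.2: "Approximately 177 patients (59 per treatment group) are to be enrolled in this study" (3 × 59 = 177). Nine scheduled dermatitis assessments as Protocol Table 3 reads (Visits 3 to 9, 11 and 12). Cumulative dose is 0 Gy when Visit 3 is graded. A level of 0.05 is stated for the primary endpoint only (SAP 3.5); I take it as two-sided. The plan gives no error rate for this analysis, so there is no figure to reproduce.

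**Assumed, not in the documents.** The share at grade ≥2 per visit and the within-patient correlation. The simulations leave out site, smoking and breast volume.

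**Step 1: closed form.** For m equally correlated records per patient, the variance of a visit average is understated by DE = 1 + (m − 1)ρ. The actual level is 2{1 − Φ(1.96/√DE)}.

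| ρ | m = 8: DE | 1.96/√DE | actual level | m = 6: actual level |
|---|---|---|---|---|
| 0.10 | 1.7 | 1.503 | 13.3% | 11.0% |
| 0.20 | 2.4 | 1.265 | 20.6% | 16.6% |
| 0.40 | 3.8 | 1.005 | 31.5% | 25.8% |

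**Step 2: null simulation.** 59 per arm, Visit 3 left out, latent-normal binary data (exchangeable or autoregressive), 5 to 55% at grade ≥2 per visit. Ordinary logistic model with treatment, visit and interaction; 1,000 runs per setting; visit-averaged contrast of one arm against vehicle.

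| Binary correlation | Rejection at nominal 5% |
|---|---|
| 0 | 4–5% |
| about 0.10–0.11 | 10–14% |
| 0.20–0.23 | 16–23% |
| 0.26–0.30 | 19–25% |
| 0.37–0.43 | 24–33% |

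The corresponding 2-df three-arm test gave 12–18% at about 0.1, 20–32% at 0.20–0.23, and up to 46%.

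**Step 3: other tests from the same model.**
- Treatment term at a single reference visit: about 1–6%.
- Interaction likelihood-ratio test with correlated records: 0–4%, so conservative.
- Joint test of treatment plus interaction: about 5–12%, or 3–7% with Visit 3 included.

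**Step 4: Visit 3.** With 59 successes and no failures per arm, each arm's log-odds is log(59/0), which is infinite, so the difference between arms is undefined. In 60 simulated trials with an all-success Visit 3, the visit-averaged treatment effect had a median standard error of 0.86 after 8 iterations and about 2,550 after 25. That number only reflects where the algorithm stops. The Wald test rejected in 0% of runs.

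Contrasts at well-populated visits survive. With an assumed 50% at grade ≥2 on the last radiation day, the standard error there is √{2/(59 × 0.25)} = 0.37, and a full-interaction fit to one simulated data set gave the same value.

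**Step 5: does clustering repair it?** Six visits with 12, 22, 35, 45, 55 and 40% at grade ≥2; 2-df visit-averaged test; 300 runs per setting.

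| Latent correlation | Ordinary model | GEE, robust SE |
|---|---|---|
| 0.30 | 19% | 4.0% |
| 0.45 | 24% | 4.7% |
| 0.60 | 32% | 6.3% |

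The Monte Carlo error near 5% is √(0.05 × 0.95/300) = 1.3 points. A separate six-visit null run over latent correlations 0.15 to 0.6 gave 11–23% for the ordinary fit, 4–6% with patient clustering, and 5–6.5% for single-visit contrasts.

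**Step 6: could empty visits simply be dropped?** If a share p is at grade ≥2, the chance that at least one of three arms has no failure is 1 − {1 − (1 − p)^59}³. For p = 3% this is 1 − (1 − 0.166)³ = 42%. For p = 5% it is 1 − (1 − 0.048)³ = 14%. A rule that drops such visits would let chance, or a real treatment effect, decide which visits are analysed.

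**The case against.** The strongest reply is that the SAP never says which treatment contrast it will take. With an interaction in the model and a bar chart by visit, by-visit comparisons are a natural reading. Each uses one record per patient and holds its level. This stands. A reader might infer that every treatment test from this model is either inestimable or inflated. Steps 3 and 4 do not support that: the inflation belongs to visit-averaged effects, and the infinite estimate to effects taken at or averaged over an empty visit.

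It also stands that the SAP may treat Visit 3 as the dermatitis baseline and leave it out. A reader might infer several visits at which grade ≥2 is impossible, but only Visit 3 precedes radiation; Visits 4 and 5 may be sparse, not empty by design. Worst-observation imputation (SAP 3.6) could even place a failure at a missed Visit 3. That would hide the separation by recording dermatitis before any radiation.

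For SAP 5.2.4, the endpoints are proportions of patients who develop a sign, possibly one record per patient, and dry desquamation is a Grade 1 feature. No size was computed there, and the figures above do not transfer.

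Finally, SAP 5.2 already advises caution with secondary p-values. That caution concerns multiple comparisons. It does not tell the reader that an individual interval may be too narrow.

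**Conclusion.** The gap is real: the model has repeated records per patient and no within-patient term. For a visit-averaged comparison of one arm with vehicle, nominal 5% becomes roughly 10–33% over assumed binary correlations of about 0.1 to 0.4 and the assumed visit rates. A single figure such as 20–25% might be inferred, but it corresponds only to part of that correlation range, and the documents give no correlation. Single-visit contrasts stay near or below nominal, and the interaction test is conservative. If Visit 3 is included and, as expected, has no failures, a treatment effect taken at or averaged over it has no finite estimate.

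This should be fixed, but it does not threaten the trial's main claim. It concerns nominal inference on secondary endpoints without formal error control. The primary model has its own subject effect.

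**What to change.** In SAP 5.2.2, and in 5.2.4 where its endpoints are modelled by visit:

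- Fit a GEE (logit link, patient as cluster, robust standard errors) or a logistic mixed model with a random patient effect, and say which. The first gives a population-averaged odds ratio, the second a patient-specific one.
- List a fixed set of visits that excludes pre-radiation Visit 3, and describe Visit 3 separately.
- For sparse cells, use Firth-type penalisation and do not remove visits according to the outcomes seen. The penalty does not handle correlation, so standard errors must still be clustered by patient.
- State the treatment contrast, for example the average over the listed visits, or named single visits.
- For 5.2.4, say whether each endpoint is one record per patient or modelled by visit.

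The cost is SAP wording and a change of procedure, with no new data. Intervals for visit-averaged effects will be wider, and correctly so, and Visit 3 will only be described.
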